10.4.2 UNANTICIPATED PROBLEM REPORTING

The Principal Investigator will report unanticipated problems (Ups) to the sponsor and the reviewing Institutional Review Board (IRB). The UP report will include the following information:

- Protocol identifying information: protocol title and number, PI's name, and the IRB project number;
- A detailed description of the event, incident, experience, or outcome;
- An explanation of the basis for determining that the event, incident, experience, or outcome represents an UP;
- A description of any changes to the protocol or other corrective actions that have been taken or are proposed in response to the UP.

This report shall be submitted as soon as possible, but in no event later than 10 working days after the investigator first learns of the effect. A sponsor who conducts an evaluation of an unanticipated adverse device effect shall report the results of such evaluation to the FDA, the reviewing IRB, and to the Principal Investigator within 10 working days after the sponsor first receives notice of the effect. Thereafter the sponsor shall submit such additional reports concerning the effect as FDA requests.

10.4.3 REPORTING UNANTICIPATED PROBLEMS TO PARTICIPANTS

Not applicable.

11 STATISTICAL CONSIDERATIONS

A formal Statistical Analysis Plan (SAP) will not be developed for this study, thus formal null and alternative hypothesis will not be stated.

11.1 STATISTICAL MEASUREMENTS

Primary Safety and Efficacy Endpoints:

1. Safety

The safety of the FUSION system will be determined by its ability to avoid hypoglycemia in adult type 1 and type 2 diabetic patients consuming three meals over a period of 24 hours. Safety will be measured by calculating the percent of all glucose values that are within the hypoglycemic range of less than 70 mg/dL.

Statistics – No statistical comparison will be made for this measurement.

2. Efficacy

The efficacy of the FUSION system will be determined by its ability to maintain glucose in the normal range in adult type 1 and type 2 diabetic patients consuming three meals over a period of 24 hours. Efficacy will be measured by calculating the percent of all glucose values that are within the normal glucose range of 70-180 mg/dL.

Statistics – No statistical comparison will be made for this measurement.

Secondary Efficacy Endpoints:

The secondary objectives of the study are to assess the controller's ability to minimize glucose curve measurements associated with increased ICU morbidity/mortality rates, and to maximize those measurements associated with decreased ICU morbidity/mortality rates.

1. Measure the percent of glucose values that are within the severe hypoglycemic range of 0- <54 mg/dL.

Statistics – No statistical comparison will be made for this measurement.

2. Measure the percent of glucose values that are within the moderate hypoglycemic range of 54-69 mg/dL.

Statistics – No statistical comparison will be made for this measurement.

3. Measure the number of hypoglycemic (< 70 mg/dL) events.

Statistics – No statistical comparison will be made for this measurement.

DEMONSTRATION OF AN ARTIFICIAL INTELLIGENCE BASED CLOSED LOOP GLUCOSE CONTROL SYSTEM AS A THERAPEUTIC MODALITY IN TYPE 1 AND TYPE 2 DIABETIC PATIENTS

Protocol IMT 2022-1

CONFIDENTIAL

Version1.0.7

22 August 2022

4. Measure the percent of all glucose values that are within the desired glucose control range of 100-140 mg/dL.

Statistics – No statistical comparison will be made for this measurement.

5. Measure the percent of glucose values that are within the range of 70-140 mg/dL.

Statistics – No statistical comparison will be made for this measurement.

6. Measure the percent of glucose values that are within the hyperglycemic range of > 140 mg/dL.

Statistics – No statistical comparison will be made for this measurement.

7. Measure the percent of glucose values that are within the range of 70-180 mg/dL.

Statistics – No statistical comparison will be made for this measurement.

8. Measure the percent of glucose values that are within the hyperglycemic range of > 180 mg/dL.

Statistics – No statistical comparison will be made for this measurement.

9. Measure the mean glucose value in mg/dL.

Statistics – No statistical comparison will be made for this measurement.

10. Measure of dispersion – coefficient of variation.

Statistics – No statistical comparison will be made for this measurement.

11. The study data will be used to determine the percentage of paired glucose values (continuous glucose monitors and the average of the two continuous glucose monitors versus the Nova StatStrip Hospital Glucose Meter System Reference glucose) in each zone using a Clarke error grid analysis.¹ No statistical comparison will be made for this measurement.

The glucose data for the above statistical analysis will be the glucose data used by the FUSION system for purposes of glucose control, unless otherwise specified.

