4.3 ASSESSMENT OF POTENTIAL RISKS AND BENEFITS

4.3.1 FAILURE OF DEXCOM G6 CONTINUOUS GLUCOSE MONITOR(S)

The risk of complete failure of the continuous glucose monitoring system will be mitigated through use of two Dexcom G6 CGM systems, which will provide redundancy to this critical component of the FUSION artificial pancreas system. In addition, replacement of the Dexcom CGM system – sensor, transmitter, or receiver – will be allowed if any of these three components of an individual CGM system experiences a failure. To clarify, the FUSION system uses a simple average of the two Dexcom G6 CGM values to decide what steps to take to bring the subject's blood glucose value into the desired control range. In order to be averaged, these two Dexcom G6 CGM values must be time stamped within 5 minutes of each other. The FUSION system will operate for up to four hours with glucose readings from only one Dexcom G6 CGM system, and for up to 20 minutes with no values from either Dexcom G6 CGM

DEMONSTRATION OF AN ARTIFICIAL INTELLIGENCE BASED CLOSED LOOP GLUCOSE CONTROL SYSTEM AS A THERAPEUTIC MODALITY IN TYPE 1 AND TYPE 2 DIABETIC PATIENTS

Protocol IMT 2022-1

CONFIDENTIAL

Version1.0.7

22 August 2022

system. The FUSION system will automatically shut down after four hours if it has only one Dexcom G6 CGM system available for use. The FUSION system will automatically shut down if it has no Dexcom G6 CGM systems available for use for a period of time exceeding 20 minutes.

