4.3.2 USE OF INNACURATE CGM GLUCOSE VALUE FOR GLUCOSE CONTROL

The risk of using an inaccurate CGM value for glucose control will be mitigated by averaging the glucose value of the two CGM devices. In addition, independent Reference Glucose Values (Nova StatStrip Hospital Glucose Meter System) will be obtained every 10-60 minutes to ensure subject safety.

The benefit of using Dexcom's G6 CGM, which has already been approved as an iCGM, is to determine its accuracy in different scenarios/settings (e.g., participants with diabetes in the proposed study; COVID-19 patients in ICU in future study).

The benefit of obtaining Reference Glucose Values every 10-60 minutes is to independently monitor for hypoglycemia in cases where the CGM systems are providing the FUSION system with false high glucose levels that could lead to hypoglycemia, or to monitor for hyperglycemia in cases where the CGM systems are providing the FUSION system with false low glucose levels that could lead to hyperglycemia. The Reference Glucose Values can be used to administer rescue doses of 50% intravenous dextrose in cases of severe hypoglycemia (< 54 mg/dL), moderate hypoglycemia (54-69 mg/dL) with associated hypoglycemia symptoms, or in cases of neuroglycopenia.

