| The secondary objectives of the study are to assess the controller's ability to minimize glucose curve measurements associated with increased ICU morbidity/mortality rates, and to maximize those measurements associated with decreased ICU morbidity/mortality rates. | 
 1. Measure the percent of glucose values that are within the severe hypoglycemic range of 0 – < 54 mg/dL. 2. Measure the percent of glucose values that are within the moderate hypoglycemic range of 54-69 mg/dL. 3. Number of hypoglycemic (< 70 mg/dL) events. Each event separated by at least one glucose value ≥ 70 mg/dL. 4. Measure the percent of all glucose values that are within the desired glucose control range of 100 – 140 mg/dL. 5. Measure the percent of glucose values that are within the range of 70-140 mg/dL. 6. Measure the percent of glucose values that are within the hyperglycemic range of > 140 mg/dL. 7. Measure the percent of glucose values that are within the range of 70-180 mg/dL. 8. Measure the percent of glucose values that are within the hyperglycemic range of > 180 mg/dL. 9. Mean glucose level (mg/dL). 10. Measure of dispersion – coefficient of variation. 11. The study data will be used to determine the percentage of the Dexcom's G6 CGM's glucose values in each zone using a Clarke error grid analysis.¹ This same calculation will be performed on the average of the two Dexcom | The chosen secondary endpoints are routinely measured in glucose control studies and serve to provide a more complete picture of the AI based glucose control systems ability to both safely and effectively provide glucose control. |

DEMONSTRATION OF AN ARTIFICIAL INTELLIGENCE BASED CLOSED LOOP GLUCOSE CONTROL SYSTEM AS A THERAPEUTIC MODALITY IN TYPE 1 AND TYPE 2 DIABETIC PATIENTS

Protocol IMT 2022-1

CONFIDENTIAL

Version1.0.7

22 August 2022

| OBJECTIVES | ENDPOINTS | JUSTIFICATION FOR ENDPOINTS |
|----------------------|---|-----------------------------|
| | G6 CGM systems used by the FUSION system for purposes of glucose control. | |
| Tertiary/Exploratory | | |
| None planned | | |

The glucose data for the above statistical analysis will be the glucose data used by the FUSION system for purposes of glucose control, unless otherwise specified.

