10.2 SAFETY AND OTHER ASSESSMENTS

10.2.1 SAFETY

The exclusion criteria which are used to screen for potential subjects eliminates those with hepatic failure, signs of significant hepatic disease as defined by an alanine aminotransferase greater than three times the upper limit of normal, any signs of renal failure, subjects with any history of congestive heart failure, subjects with a history of ischemic heart disease/cerebrovascular accident/seizures and eliminates all females who are pregnant. The purpose of these exclusion criteria is to avoid first in human trials on subjects with severe organ compromise, and exposure of a fetus to an untested medical device.

Independently monitoring Reference Glucose Values every 10-60 minutes will ensure subject safety should they experience hypoglycemia that the closed loop glucose control system is either unaware of or is unable to effectively treat. This monitoring will allow for early intervention in case the subjects experience severe hypoglycemia (Reference Glucose Value < 54 mg/dL) or moderate hypoglycemia (Reference Glucose Value 54-69 mg/dL) with clinical signs of hypoglycemia.

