| 15. | 
Obtain Reference Glucose Values using the Nova StatStrip Hospital Glucose Meter System every 10-60 minutes from time 4 to 32 hours according to the following guidelines:
 
A. Every 10 minutes: Monitor the subject's Reference Glucose Values every 10 minutes whenever either of the following occur:
 
I. Either of the Dexcom G6 CGM's is less than 70 mg/dL.II. When the most recent Reference Glucose Value is less than 70 mg/dL. 
Discontinue every 10 minute Reference Glucose Value monitoring when both of the following have occurred:
 
I. Both Dexcom G6 CGM's are greater than 70 mg/dL.II. The subjects have two consecutive Reference Glucose Values greater than 70 mg/dL. These Reference Glucose Values will be measured by the Nova StatStrip Hospital Glucose Meter System on either a venous or capillary blood sample. 
B. Every 30 minutes: Monitor the subject's Reference Glucose Values every 30 minutes when the following occur:
 
I. After both Dexcom G6 CGM's begin to return glucose readings after their original insertion and prior to the onset of the closed loop glucose control session, for purposes of verifying the accuracy of the CGM's. This monitoring prior to the onset of the closed loop glucose control session may be discontinued once both CGM's have met the following CGM Validation Criteria on two consecutive Reference Glucose Values: 
CGM readings must be within ± 20 mg/dL of the Reference Glucose Value for CGM readings < 100 mg/dL or CGM readings must be within $\pm 20\%$ of Reference Glucose Values for CGM readings ≥ 100 mg/dL on two consecutive Reference Glucose Values.
 
II. During the first 2 hours of the closed loop glucose control session (time 5-7 hours).III. When either Dexcom G6 CGM has a glucose reading less than 85 mg/dL displayed on either the Dexcom G6 Receiver or the Dexcom G6 Follow App.IV. During periods of severe hyperglycemia, which is defined as a CGM or Reference Glucose Value greater than 240 mg/dL.V. When only one Dexcom G6 CGM is available for use by the FUSION system for glucose control.VI. After a CGM has been replaced, and until the replaced CGM has met the above noted CGM Validation Criteria.VII. When the subject experiences any signs of neuroglycopenia, regardless of the glucose level displayed by the CGM's.VIII. From time 29-32 hours, which is the 3 hour time period after conclusion of the closed loop glucose control session. |

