|-----|---|

| | |
|-----|--|
| | 
C. Every 60 minutes: Monitor the subject's Reference Glucose Value every 60 minutes when the following occur:
 
During the last 22 hours of the closed loop glucose control session (time 7-29 hours), if the following occur:
Both CGM's are in the range of 85-240 mg/dL and the subject is not experiencing any signs of neuroglycopenia. 
Result: _____ mg/dL, Time: _____ (24 hour clock) Note: Notify study team if the CGM or Reference Glucose Value is < 70 mg/dL or > 300 mg/dL.
 |
| 16. | 
Dexcom G6 CGM Placement, Calibration and Replacement
 
Visit 3 (Time 0 to 5 hours): Place two Dexcom G6 CGM's in the abdomen 5 cm to the right and left of the umbilicus (Figure 28).
  
18 years and older
 
Figure 28 – Green shaded areas denote appropriate areas of the abdominal wall to place the Dexcom G6 CGM's. This figure is from the Dexcom G6 CGM user manual.
 |

Make sure the Dexcom G6 Transmitters are labeled “#1” and “#2”. These labels should be in a clearly visible position after the Transmitters have been attached to the Dexcom G6 glucose sensors. Once both Dexcom CGM’s begin to return glucose values, obtain a Reference Glucose Value using the Nova StatStrip Hospital Glucose Meter System. If either of the Dexcom CGM’s do not meet CGM Validation Criteria, they may be calibrated. The Dexcom G6 CGM’s must meet the following CGM Validation Criteria throughout the CRC study session (visit 3), otherwise they will be calibrated as often as is necessary:

1. CGM readings must be within ± 20 mg/dL of the Reference Glucose Value for CGM readings < 100 mg/dL or CGM readings must be within $\pm 20\%$ of Reference Glucose Values for CGM readings ≥ 100 mg/dL on two consecutive Reference Glucose Values.

Calibrations should only be attempted when the glucose rate of change is less than ± 2 mg/dL/min on the Dexcom G6 CGM (see figure 29).

If after two calibration attempts prior to beginning the closed loop glucose control session (time 0-5 hours) the CGM(s) still do not meet CGM Validation Criteria, they may be replaced. The closed loop glucose control session may not begin until there are two working Dexcom G6 CGM’s in place, and both CGM’s have met the above noted CGM Validation Criteria.

Closed Loop Glucose Control Session (Time 5 to 29 hours):

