| 19. | 
Meal Challenge Protocol
 
Time 5 hours (~1200 on day 1): Subject to consume lunch with 60 grams of carbohydrate.
 
Time 11 hours (~1800 on day 1): Subject to consume dinner with 75 grams of carbohydrate.
 
Time 25 hours (~0800 on day 2): Subject to consume breakfast with 50 grams of carbohydrate.
 
Carbohydrates should make up 45-60% of the total Kcal's of each meal.
 
Time 5 to 29 hours: Closed loop control of blood glucose with FUSION system (Figure 20), to control range of 100-140 mg/dL.
 
Throughout the entirety of the subjects stay in the CRC (e.g., time 0 to 32 hours), if the subject has a Reference Glucose Value less than 70 mg/dL or is experiencing signs of neuroglycopenia (hypoglycemia of sufficient duration and degree to interfere with normal brain metabolism and function) at any Reference Glucose Value, they will be offered snacks and/or glucose containing juice.
 |
| 20. | 
RECOVERY PERIOD (Time 29 to 32 hours)
 
1. Type 1 Diabetic Subjects:
 
Type 1 diabetic subjects will be required to have four consecutive Reference Glucose Values within the range of 80-250 mg/dL, with the most recent rate of change being less than ± 2 mg/dL/min, which is equal to either a single sideways arrow or a single up or down arrow as noted in the illustration above (Figure 29), which was taken from Dexcom G6 CGM manual.
 
The glucose sample source can be either from a venous catheter sample, or from a capillary fingerstick. The Nova StatStrip Hospital Glucose Meter System will be used to analyze the sample for glucose.
 
Following standard practice, subjects with type 1 diabetes will receive a dose of basal insulin dose two hours before discontinuation of the FUSION systems continuous insulin infusion (CII), as it is expected that basal insulin levels will slowly reach a therapeutic level after administration. An endocrinologist ([name] or [name]) will determine the dose of the basal insulin before CII discontinuation for subjects with type 1 diabetes. The next dose of basal insulin (at home) and transition to the participants home regimen will be determined by [name] or [name].
 |

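### No planned statistic counts Reference Glucose Values below 70 mg/dL, so an asymptomatic Reference low of 54-69 that the controller's CGM signal misses is not assured of a place in the safety summary

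*Combined protocol and SAP*

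**What the plan says.** Section 11.1 measures safety as the share of glucose values below 70 mg/dL and fixes the data source in its closing sentence: "The glucose data for the above statistical analysis will be the glucose data used by the FUSION system for purposes of glucose control". The sentence then allows for exceptions specified elsewhere. Section 5 has the same rule: "The glucose data for the above statistical analysis will be the glucose data used by the FUSION system". Under section 4.3.1 that glucose is the simple average of two Dexcom G6 CGMs, and "The FUSION system will operate for up to four hours with glucose readings from only one Dexcom G6 CGM system".

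Reference Glucose Values (bedside meter, at least hourly) go on the case report form. The controller does not use them except through CGM calibration (section 8.1.1.4). Section 4.3.2 says they are there to detect hypoglycemia "in cases where the CGM systems are providing the FUSION system with false high glucose levels that could lead to hypoglycemia". Section 10.2.1 says they guard against "hypoglycemia that the closed loop glucose control system is either unaware of or is unable to effectively treat".

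Protocol 2 (IMT2022-1-P2) acts on a Reference below 70 whether or not there are symptoms:
- Item 15A moves draws to every 10 minutes: "When the most recent Reference Glucose Value is less than 70 mg/dL".
- Item 15C says: "Notify study team if the CGM or Reference Glucose Value is < 70 mg/dL or > 300 mg/dL".
- Item 19 offers a snack or juice "if the subject has a Reference Glucose Value less than 70 mg/dL or is experiencing signs of neuroglycopenia".

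**The concern.** The signal that scores safety is the signal whose error would cause the harm. If the sensors read high, the controller and the primary safety result miss the same low. The protocol foresees this and collects an independent measurement to detect it, but no planned statistic counts the lows that this measurement finds.

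Section 11.1 asks whether the system avoids hypoglycemia. The planned number answers whether the controller's input stayed at or above 70. A subject could have a meter value in the 50s or 60s, be offered juice for it, and contribute 0% below 70 and no hypoglycemic event.

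Sensor error can also run low, as with the compression artifact in section 4.3.3. A Reference-based view could therefore make the safety picture look better or worse.

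**Working it through.** The plan has no alpha, power or sample-size figure to reproduce (sections 11 and 11.2). The check has three parts.

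**1. Where could a Reference of 54-69 be counted?** Take a subject without symptoms, with intravenous access in place and controller glucose at or above 70.

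| Planned output | Source or condition | Counts the event? |
|---|---|---|
| Share below 70 (11.4.2, 11.4.4) | Controller glucose; no other source named | No |
| Shares below 54 and 54-69; number of events below 70 (11.4.3) | Controller glucose | No |
| Clarke grid (11.1, 11.4.3) | Reference paired with each CGM and with the average | A point on the graph and part of a zone percentage; not a count of lows or of subjects |
| Termination and severe event (9.1, 10.3.3.1) | Reference below 54 | No |
| Rescue medicine, percent of subjects (8.5.1, 11.4.4) | At 54-69, needs symptoms | No; snacks and juice are listed separately from the rescue medications |
| Adverse events, percent of patients (10.3.1, 10.3.4, 11.4.4) | Broad definition; event not named in the severe list or on the SAE form | Only if the investigator records it |
| Individual data tabulation (11.4.8) | Not applicable | No |

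Section 4.1 gives glucagon at any Reference below 70 once intravenous access is lost, with no symptom condition. Section 8.5.1 does not list that condition. The two sections must be reconciled, but either way the case above has access in place.

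**2. Do the protocol's checks allow the case?** Under section 8.1.1.4, a CGM below 100 is recalibrated only if it differs from Reference R by more than 20 mg/dL. Passing CGM values at or above 70 therefore run from 70 to R + 20:
- R = 54: 70 to 74
- R = 60: 70 to 80
- R = 69: 70 to 89

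A CGM of 100 or more must be within 20% of R. At R = 69 the limit is 0.2 × 69 = 13.8, so 100 fails. If both CGMs pass, their average is also at most R + 20. Two equal readings do not trigger the alarm for CGMs more than 20% from their average. So every R from 54 to 69 can be scored at or above 70 with no recalibration.

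In reverse, passing values below 70 run from R − 20 to 69:
- R = 70: 50 to 69
- R = 89: 69 only
- R = 90: none, since the lower limit is 70

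So every R from 70 to 89 can be scored below 70. These are possibilities, not probabilities.

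**3. What would one case look like?** Assume one asymptomatic Reference of 60, both CGMs at 75 (difference 15, within 20), and no other low value.
- Controller readings in 24 hours: 1440 / 5 = 288 (144 on a 10-minute cycle).
- Planned result: 0 / 288 = 0% below 70, no events, no rescue medicine.
- Reference-based result: one subject below 70, none below 54, one discordant pair.

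**Data at hand.** With no triggers, item 15 schedules draws at 0, 30, 60, 90 and 120 minutes (5), then hourly at hours 3 to 23 (21): 5 + 21 = 26 per completed session. If all eight subjects complete, 26 × 8 = 208. A subject stopped early has fewer but stays in the analysis (section 11.3).

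**The case against.** The strongest reply is that the event is neither invisible nor unmanaged. Much of that stands.

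- **The Clarke analysis is graphed as well as tabulated**, and it includes the two-CGM average. The discordant pair would be visible as a point. It would still not show how many subjects had a low.
- **The event may be an adverse event.** Section 4.1 defines hypoglycemia as any value below 70 and calls it the main risk. Section 10.3.1 is broad, section 10.3.4 requires documentation, and section 11.4.4 reports each event. A reader might infer that the event can enter no count at all. The documents do not support that. They leave the count to the investigator's judgment.
- **Bedside oversight is dense.** CGM alarms are set below 85. At Reference 54-64, any passing CGM reads at most 84 and so falls under that trigger. An Independent Safety Monitor reviews cumulative data (section 12.1.6), and all records are checked before the next session (section 12.1.7). Inferring a hole in subject protection would be wrong.
- **The Reference is imperfect.** Section 8.1.1.4 cites 1614/1894 = 85.2% of meter specimens below 75 mg/dL as compliant in the second evaluation, so 280/1894 = 14.8% were not; the criterion is not given. Samples may also change from venous to capillary (sections 4.1 and 4.3.5). Some discordant pairs may be meter error.
- **The study is descriptive**, with eight subjects, no formal SAP and an openly declared data source. That limits the weight of the point but does not remove it.

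**Conclusion.** The point holds as a cheap improvement to reporting. The absence of any planned count of Reference values below 70 follows directly from the text and is certain. The exposed case is narrow: Reference 54-69, no symptoms, intravenous access in place, controller glucose at or above 70. It is reachable because the checks tolerate 20 mg/dL either way. How often it would happen is unknown: the documents give no frequency for either direction of disagreement.

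A reader might also infer that the zero below 70 cited in section 4.1 for the two-subject study hid lows in the same way. Section 4.1 does not name that figure's glucose source, so the inference is unsupported. Nor do the documents show that the CGM-based result must flatter the device, since the same tolerance lets a Reference of 70-89 be scored as low.

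**What to change.** Keep the CGM-based endpoints. In sections 5, 11.1 and 11.4.4, pre-specify beside the primary safety result, from start to end of AI controller use:

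1. The number of subjects with any Reference below 70 mg/dL, and with any below 54.
2. The number of pairs, and of subjects, with Reference below 70 and controller glucose at or above 70, and the same for the reverse. Pair each Reference with the last controller glucose at or before the draw, within a stated maximum age (for example 5 minutes, or 10 if that is the controller cycle). Using only earlier values keeps a recalibration made after the draw from erasing the disagreement.
3. The number of Reference values, and of those below 70, with no controller glucose inside that window. The system may run up to 20 minutes without a CGM value (section 4.3.1). These values still count in item 1.

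Present these with the CGM-based result as descriptive counts with no decision rule, and report the sample source (venous or capillary). A Reference-based percent of time is not needed.

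**Cost.** A few sentences and table rows, and no added procedures. Reference values are already on the case report form; sample source may need one field if it is not there.

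**Limits to state.** At-least-hourly draws can miss short lows: with no trigger, a 50-minute low between two hourly draws gives 0 of 26 values below 70. Trigger-driven draws make sampling uneven, so neither the subject counts nor the pair counts should be read as rates. Some discordant pairs may be meter error or follow a change of sample source.
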